#### 10. STUDY CONDUCT

#### 10.1. Overview

This is a randomized, double-blind, placebo-controlled study. The duration of a subject's participation in this study is dependent on the timing and frequency of on-study acute attacks eligible for treatment with study drug. Assuming that subjects will have 1 eligible attack every 4 weeks, it is anticipated that minimally a subject's participation would be approximately 19 weeks (inclusive of the screening period, wash-out periods of 10 to 14 days in duration in between treated attacks, and a final follow-up visit [at least 16 days after the third attack]). Each eligible subject who consents to participate in the study will receive a total of 2 single doses of BCX7353 and 1 dose of matching placebo. All subjects will undergo a screening period of up to 35 days, and 4 clinic visits; visits will occur at Baseline, within 10 to 14 days after the first and second study drug treated attacks, and at least 16 days following the last study drug treated attack. Subjects who consent to the optional observational substudy after the last study visit (Post-Attack 3 visit) will participate in study activities for approximately 12 additional weeks.

After the Baseline visit, at the first symptom of swelling or pain associated with an attack, the subject will be asked to phone the on-call study Investigator (or designee) who will review the subject's symptoms by phone and confirm that they constitute an appropriate acute attack that qualifies for treatment with study drug, including ensuring that the subject is in an environment that he/she deems suitable for completion of the timed diary. Following confirmation by the Investigator, subjects should use study drug to treat the HAE attack, within approximately 1 hour from the onset of the first symptoms.

Subjects will fill out a diary questionnaire and a 3-component VAS on a 100 mm scale for abdominal pain, cutaneous pain, and cutaneous swelling prior to and at 1, 2, 3, 4, approximately 8, and at 24 hours after record of study drug administration.

If the subject prematurely discontinues from the study, they will be requested to attend an early termination visit.

#### 10.2. Schedule of Assessments

The schedule of assessments for this study is summarized in Table 4; the optional substudy assessment schedule can be found in Table 5.

 Table 4.
 Schedule of Assessments for Study BCX7353-202

	Screening  Day  -35 to -1	Baseline	Attack 1 Telephone Contacts	Post- Attack 1 Visit (10- 14 days)	Attack 2 Telephone Contacts	Post- Attack 2 Visit (10- 14 days)	Attack 3 Telephone Contacts	Post- Attack 3 Visit/ Follow-up (16 days + 3 days)	Early Termination Visit
Informed consent a	X							X	
Telephone contact b	X		X		X		X		
Clinic visits c	X	X		X		X		X	X
Inclusion/Exclusion criteria	X	X							
Medical history	X	X							
HAE attack frequency confirmation	X								
HAE medical and medication history	X								
Height/Weight/BMI	X	$X^{d}$							$X^d$
Drugs of abuse screen e	X								
HIV/HCV/HBV serology	X								
FSH f	X								
C1 INH function and C4	X								
Pregnancy test g	X	X		X		X		X	X
Safety laboratory evaluations and urinalysis testing h	X	X		X		X		X	X
Troponin I & Troponin T		X		X		X		X	X
CK-MB		X		X		X		X	X
C3		X							
C1 INH antigen level		X							

	Screening Day -35 to -1	Baseline	Attack 1 Telephone Contacts	Post- Attack 1 Visit (10- 14 days)	Attack 2 Telephone Contacts	Post- Attack 2 Visit (10- 14 days)	Attack 3 Telephone Contacts	Post- Attack 3 Visit/ Follow-up (16 days + 3 days)	Early Termination Visit
Randomization i	X								
Physical examination	X	X		$X^{j}$		$X^{j}$		$\mathbf{X}^{\mathrm{j}}$	$\mathbf{X}^{\mathrm{j}}$
$ECG^k$	X	X		X		X		X	X
Vital signs 	X	X		X		X		X	X
Diary dispensing/ instruction/review/ collection m	X	X	X	X	X	X	X	X	X
Diary completion	+								
Concomitant medications	X	X	X	X	X	X	X	X	X
AE assessment	X	X	X	X	X	X	X	X	X
Study drug dispensing/accountability and reconstitution instruction n		X		X		X		X	X
TSQM°		X		X		X		X	

a Signing of informed consent may occur in advance of the screening visit, which is defined as the visit where site-conducted screening procedures are performed. Informed consent for the observational substudy may be obtained at the follow-up visit or earlier.

b Screening telephone contact: Subjects are instructed to contact the site as soon as they become aware of the onset of symptoms of pain or swelling associated with an HAE attack during the screening period. The on-call Investigator (or designee) will review the subject's symptoms by phone and confirm the date of the call. The Investigator may fill out a form to document the conversation. Approximately 4 hours after the initial call, the subject will again contact the on-call Investigator as is expected during the study.

Attack 1, 2, 3 contact: Subjects are instructed to contact the on-call Investigator (or designee) as soon as they become aware of the onset of symptoms of pain or swelling associated with a potentially protocol-qualified HAE attack. The on-call Investigator (or designee) will review the subject's symptoms by phone and confirm that they constitute an acute attack that qualifies for treatment with study drug, including ensuring that the subject is in an environment that he/she deems suitable for completion of the timed diary. The Investigator will fill out a form to document the conversation. Following treatment of the attack, the subject will again contact the on-call Investigator (or the Investigator will contact the subject) at least 4 hours after treatment with study drug to review the subject's response to treatment and to confirm adequate documentation of the attack in the Diary. The on-call Investigator (or designee) will call

# BioCryst Pharmaceuticals, Inc. CONFIDENTIAL

BCX7353

- the subject if the subject has not contacted the on-call Investigator (or designee) within 4-5 hours of the initial phone call. A follow-up visit to the clinic will be scheduled. Sites must attempt to contact subjects every 7 days from the last clinic visit to inquire about the occurrence of an attack.
- c Clinic visits are scheduled for Screening, Baseline and 10 to 14 days following the first and second attack treated with study drug. The Post-Attack 3 visit suffices as the end of study visit and will be held approximately 16 days after the third attack. Study drug cannot be authorized for administration for at least 14 days from a previously treated attack.
- d Weight only.
- e Analytes to be measured can be found in Table 6.
- f Follicle-stimulating hormone will be measured in women declaring themselves postmenopausal  $\leq 2$  years.
- g A serum pregnancy test will be administered to women of childbearing potential or who are postmenopausal  $\leq 2$  years at screening; all other pregnancy tests performed during the study may be urine pregnancy tests (for women of childbearing potential only).
- h Safety laboratory parameters and urinalysis testing as described in Table 6.
- i Randomization to a treatment sequence should occur prior to or during the Baseline visit, following confirmation of eligibility and Sponsor approval.
- Post-baseline, physical examinations will be targeted to reported signs and symptoms.
- k ECGs will be captured as single assessments. Any scheduled blood draws should occur after obtaining the ECG. Subjects should rest quietly for 10 minutes in a supine position prior to ECGs being performed.
- 1 Vital signs include measurement of heart rate, blood pressure and temperature.
- m Diaries will be dispensed at Screening, Baseline, and Post-Attack Visits 1 and 2. The Investigator (or designee) will provide diary instruction at Screening and will review diary entries on an ongoing basis. During each visit, any issues warranting diary re-education must occur on an as-needed basis. The completed diary will be collected at Baseline and Post-attack Visits 1 to 3. For subjects participating in the observational substudy, a diary will be dispensed at the Post-Attack 3 visit.
- n Subject will be dispensed study drug for self-administration at Baseline, Post-Attack 1 visit and the Post-Attack 2 visit. Reconstitution and dosing instructions will be reviewed with the subject. Accountability will be conducted at the Post-Attack visits.
- At baseline, the TSQM will be completed in reference to the subject's currently used acute attack medication prescribed/authorized by their HAE treater; at each subsequent study visit, the TSQM will be completed in reference to the attack previously treated with study drug.

Table 5.	Schedule of Assessments for Optional Ob	servational Substudy
	1	•

	Post-Attack 3 Visit	Week 4 of Observational Period a	Week 8 of Observational Period a	Week 12 of Observational Period a
Informed consent b	X			
Telephone contact c		X	X	X
Clinic visits	X			
Diary dispensing/instruction/review/collection d	X	X	X	X
Diary completion		4	•	
AE assessment	X	X e	X e	X e

- a The 12-week observational period begins from dispensation of HAE diary for recording of all attacks after completion of the Post-Attack 3 visit.
- b Signing of informed consent for the optional observational study may occur at the Post-Attack 3 visit or any time prior to this visit. Subjects will be asked to participate in the substudy following completion of Post-Attack 3 visit if approved by the Sponsor.
- c During the substudy, subjects will be primarily contacted via telephone; however, a clinic visit is allowed to replace the telephone contact if warranted.
- d Diaries to record details of all HAE attacks occurring after the Post-Attack 3 visit will be dispensed at the Post-Attack 3 visit and as needed thereafter. Completed diaries will be collected from the subject (in-person or via post) approximately every 4 weeks. The Investigator (or designee) will provide diary instruction at the Post-Attack 3 visit and will review diary entries upon collection for correct completion and follow-up with the subject as needed.
- e Only AEs assessed as possibly, probably or definitely related to the previously taken study drug administered will be recorded.

# 10.3. Study Visits

## 10.3.1. Screening

Prospective subjects should be screened within 35 days prior to baseline.

Written informed consent must be obtained from each subject before initiation of any screening assessments or procedures. Each subject will receive a copy of the signed and dated study-specific informed consent form (ICF). Prospective subjects who have signed an ICF who are interested in participation in the study will then undergo assessments at a Screening visit to determine eligibility. Signing of the ICF may occur prior to the screening visit, which is defined as the visit where site-conducted screening procedures are performed.

The Investigator (or designee) will conduct the following assessments at the screening visit, including:

- Review of inclusion and exclusion criteria
- Review of HAE attack frequency documentation
- HAE, medical, and medication history
- Complete physical exam

- 12-lead ECG
- Height/weight/body mass index (BMI) estimation
- Vital signs (blood pressure, heart rate, temperature, and respiratory rate)
- Serum pregnancy test for female subjects of child-bearing potential
- Blood collection for clinical chemistry, hematology, coagulation, HBV/HIV/HCV serology, C4 and C1 INH functional level, FSH (for women who declare that they have been postmenopausal ≤ 2 years)
- Urine collection for urinalysis and drugs of abuse screen
- Recording of AEs and concomitant medications
- Dispensing of HAE attack diary and any applicable subject instruction sheets
- Instructions on procedures to take during at least one HAE attack during the screening period: phoning the on-call Investigator (or designee) at the outset of HAE-associated pain or swelling, completing the diary, and placing a second call to the on-call Investigator (or designee) approximately four hours after the initial call.

All screening procedures are outlined in Table 4 and are described in Section 11.

A subject will be randomized to a treatment sequence at or prior to the Baseline visit. Subject randomization will occur after the subject has been fully determined to be eligible during screening (see Section 9.3.2).

If the Investigator has not received a call for an HAE attack through Day 35 of the screening period, the subject is considered a screening failure. If agreed by the Sponsor or designee, subjects having an attack late in the course of the screening period may prolong the screening period beyond 35 days to allow for randomization and shipment time of study drug to the clinical site, if applicable.

Rescreening of ineligible subjects, where there is a reasonable expectation that the subject will become eligible, will be approved or denied on a case-by-case basis with the Sponsor. Any screening ECGs may be repeated if the results suggest operator or machine error. Retesting of specific laboratory tests within the screening period without entirely rescreening a subject is permitted.

A reason for screen failure will be recorded in the screening eCRF for all subjects who do not enter the study.

#### **10.3.2.** Baseline

Subjects who meet all study eligibility criteria, who agree to participate, have demonstrated competence in phoning an investigator for an HAE attack and completing an attack diary during the screening period and who are authorized for randomization by the Sponsor will be asked to return for a Baseline visit. Inclusion/ exclusion criteria will be reviewed to ensure continued subject eligibility. Subjects are asked to fast overnight for at least 8 hours prior to the blood draw for laboratory testing.

The following assessments will be completed:

- Review of inclusion and exclusion criteria
- Review of medical history
- Review of concomitant medications
- Administration of the TSQM (the TSQM will be completed in reference to the subject's currently used acute attack medication prescribed/authorized by their HAE treater)
- Weight
- Vital signs (heart rate, blood pressure and temperature)
- 12-lead ECG
- Complete physical exam
- Assessment of any AEs that occurred since the Screening visit
- Urine collection for urinalysis and urine pregnancy test for female subjects of child-bearing potential
- Blood collection for clinical chemistry, hematology, and coagulation
- Blood collection for C1 INH antigen level, C3, CK-MB, Troponin I, and Troponin T
- Study drug dispensing for treatment of an acute HAE attack by self-administration
- Instruction on reconstitution of study drug and administration
- Screening HAE diary collection and review
- HAE diary dispensing for recording Attack 1, daily HAE diary and any applicable subject instruction sheets
- Instructions on treatment of attacks by self-administration with study drug. Subjects should also be taught to record start and stop time and treatment of any additional HAE attacks that occur following the Baseline visit.

#### **10.3.3.** Telephone Contacts

Subjects will be instructed to contact site personnel at the first symptom of swelling or pain associated with a potentially protocol-qualified HAE attack, and if treated with study drug, at approximately 4 hours following treatment. If the subject has not contacted the on-call study Investigator (or designee) within 5 hours, the on-call Investigator will call the subject. The on-call Investigator (or designee) will review the treatment and progression of the HAE attack with the subject and document the conversation. Subjects who did not require standard of care at 4 hours will be reminded at the telephone call by the Investigator that they may use standard of care at any time point at their own discretion if not experiencing improvement or who are experiencing progression of the HAE attack. Subjects will also be reinstructed on diary completion. AEs and concomitant medications will also be collected by phone. Exceptions to the return phone call at 4 hours are discussed in Section 11.2.2.

The site staff will schedule a clinic visit within 10 to 14 days after the administration of study drug and remind the subject to bring their HAE attack diary and study drug containers to their next visit.

Sites must attempt to contact subjects approximately every 7 days from the last clinic visit (i.e., after the Baseline visit, Post-Attack 1 clinic visit, and Post-Attack 2 clinic visit) to inquire about the occurrence of an attack if the subject has not contacted the site during this time frame.

#### 10.3.4. Clinic Visits Following Study Drug Administration

Subjects will return to the clinic following the administration of study drug to treat an acute attack. Subjects will attend a total of 3 on-study clinic visits: Post-Attack 1 clinic visit, Post-Attack 2 clinic visit, and Post-Attack 3 clinic visit. After Attack 1 and Attack 2, subjects will return to the clinic 10-14 days after administration of study drug. Subjects will not be authorized to treat a subsequent attack until at least 14 days have elapsed since the last study drug administration. After Attack 3, subjects will return to the clinic for a follow-up visit 16 days after their last use of study drug (visit window permissible up to 19 days).

The following assessments will be performed at each visit:

- Targeted physical examination
- Vital signs (blood pressure, heart rate and temperature)
- 12-lead ECG (including comparison of QTcF to Baseline value)
- Review of concomitant medications and AEs
- Administration of TSQM questionnaire (TSQM will be completed in reference to the attack previously treated with study drug)
- Blood collection for clinical chemistry, hematology and coagulation
- Blood collection for CK-MB, Troponin I and Troponin T
- Urine collection for urinalysis and urine pregnancy test for female subjects of child-bearing potential
- Study drug accountability
- Post-Attack 1 and 2 clinic visits only: dispense study drug
- Collection of subject-completed HAE attack diary and review
- Post-Attack 1 and 2 clinic visits only: HAE diary dispensing for recording Attacks 2 and 3, daily HAE diaries and any applicable subject instruction sheets
- Review/re-education, as applicable, of completion of HAE attack diary, dosing instructions, phone call(s) to investigators (Post-Attack 1 and 2 clinic visits only). Subjects should record start and stop time and treatment of any additional HAE attacks that occur prior to the Post-Attack 3 visit.
- Post Attack 3 visit, for those participating in the optional observational study:

- Signing of informed consent for participation in the optional observational study (consent may be signed prior to this visit)
- Instruct and dispense diary to record details of any HAE attacks that occur

#### **10.3.5.** Early Termination Visits

Subjects who discontinue treatment early (i.e., prior to the treatment of 3 acute attacks) must complete an early termination visit as outlined in Section 10.3.5.

Assessments to be performed at this visit are described in Section 11. In the event that there are clinically significant findings from safety assessments that are ongoing at the time of the visit, the subject will be followed at additional unscheduled study visits until the findings are resolved or stabilized at a new baseline.

The following assessments will be performed at the early termination visit:

- Subject weight
- Targeted physical examination
- Vital signs (blood pressure, heart rate and temperature)
- 12-lead ECG (including comparison of QTcF to Baseline value)
- Review of concomitant medications and AEs
- Blood collection for clinical chemistry, hematology, and coagulation
- Urine collection for urinalysis and urine pregnancy test for female subjects of childbearing potential
- Blood collection for CK-MB, Troponin I and Troponin T
- Study drug accountability
- Review and collection of the diary

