#### 8.3.2. Subject Discontinuation from Study Drug

A subject will be withdrawn from study drug for any of the following bulleted reasons, which will be recorded in the source documents and eCRF. In all cases, subjects who discontinue study drug will be requested to complete an Early Termination visit and all procedures as outlined in Section 10.3.5.

- Intercurrent illness or emergence of a new illness/medical condition that would, in the judgment of the Investigator, affect assessments of clinical status to a significant degree
- Subsequent determination that inclusion/exclusion criteria were not met
- Emergence of any laboratory abnormality or AE that in the judgment of the Investigator compromises the ability to continue study-specific procedures or is considered not to be in the subject's best interest due to an altered risk/benefit profile
- Subject noncompliance with study drug or to the protocol
- Discontinuation at the request of the Sponsor, competent authorities in the Member State(s) concerned, or the institutional review board (IRB)/independent ethics committee (IEC)
- Criteria outlined in Sections 8.3.2.1 and 8.3.2.2.

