# 11.2. Subject-Completed Assessments

#### 11.2.1. Treatment Satisfaction Questionnaire

To assess treatment satisfaction of the medication a TSQM will be administered once at Baseline and at each clinic visit following treatment of an acute attack with study drug. At Baseline, the TSQM will be completed in reference to the subject's currently used acute attack medication prescribed/authorized by their HAE treater; at each subsequent study visit, the TSQM will be completed in reference to the attack previously treated with study drug

For all subject-completed forms, clinic staff should ensure the subject reads the instructions and completes the questionnaires in full prior to filing in the source documentation.

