# 13.3.5. Subject Satisfaction Analyses

The change from baseline in the TSQM global satisfaction score as well as effectiveness, side effects, and convenience subscales will be summarized. Data will be listed, summarized, and appropriately tested for differences between active treatment and placebo and between active and current acute therapy utilized at baseline.

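### The early termination visit list and that column of Table 4 omit the TSQM that other protocol text calls for, so a dose's satisfaction score can be lost if a subject stops before its Post-Attack visit

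*Protocol*

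**What the plan says.** Two places leave the TSQM out of the early termination visit. Protocol 10.3.5 opens its list with "The following assessments will be performed at the early termination visit" and gives ten items, none of them the TSQM. In Table 4 the TSQM row is marked at Baseline and at the Post-Attack 1, 2 and 3 visits, and the Early Termination cell is empty. The row directly above it, study drug dispensing and accountability, is marked in that column.

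Other text reads more widely. Section 11.2.1 says that "a TSQM will be administered once at Baseline and at each clinic visit following treatment of an acute attack with study drug". The Table 4 footnote to the TSQM row says that "at each subsequent study visit, the TSQM will be completed in reference to the attack previously treated with study drug". Section 10.3.5 itself adds: "Assessments to be performed at this visit are described in Section 11", and 11.2.1 is part of Section 11. Section 8.3.1 asks subjects who withdraw consent to use the early termination visit to complete the end-of-study evaluations, and the end-of-study visit (Post-Attack 3) includes the TSQM.

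On who attends, 8.3.2 says that "subjects who discontinue study drug will be requested to complete an Early Termination visit and all procedures as outlined in Section 10.3.5", and 10.3.5 says that "Subjects who discontinue treatment early (i.e., prior to the treatment of 3 acute attacks) must complete an early termination visit". Neither section says whether this visit replaces a Post-Attack visit that is still due or comes in addition to it.

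On use of the scores, subject satisfaction is a secondary objective (6.1) and the TSQM is listed under other secondary endpoints (7.2.3). Under 13.3.5 the data are to be "appropriately tested for differences between active treatment and placebo and between active and current acute therapy utilized at baseline".

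**The concern.** The list in 10.3.5 and the schedule in Table 4 are what a site works from on the day. A site following either would let a subject go home without the questionnaire, although the subject is in clinic and is handing back the diary for the attack just treated. A score not taken then cannot be recovered at analysis.

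The subjects concerned have stopped early, so their missing scores are unlikely to resemble those of subjects who continued. Stops soon after a dose are foreseeable. Rash is to be evaluated within 24 to 36 hours of awareness (11.1.11), and a study-drug-related Grade 3 or 4 rash ends dosing (8.3.2.2). Section 5.4.4.2 reports that one subject in Study BCX7353-101 stopped after a single 500 mg dose because of diarrhoea and abdominal pain. Subjects who withdraw because of a treatment-emergent adverse event may not be replaced (8.1).

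Section 13.3.5 gives no rule for a missing score. Section 13.3 leaves missing data to the SAP, but the SAP supplied covers a different study (BCX7353-302), so the handling cannot be checked.

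**Working it through.** The protocol has no figure of its own to reproduce: 13.1 states that the sample size was not based on statistical considerations, and no dropout rate or TSQM variance is given. The check therefore asks which doses can lose a score, and then how far a lost score could move a mean.

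**Which doses are exposed**

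- Under 10.3.4 the TSQM is given at each Post-Attack visit for the attack just treated. For doses 1 and 2 that visit falls 10 to 14 days after dosing. A dose whose Post-Attack visit has taken place is already scored.
- Section 10.3.5 defines early discontinuation as stopping before three attacks have been treated. A subject who has treated the third attack goes on to the Post-Attack 3 visit, where the TSQM is given.
- Scheduled post-dose ECGs and laboratory tests are first done at the Post-Attack visit. Stops triggered by those results would normally already have a score.
- What remains is a stop between dose 1 or 2 and its 10 to 14 day visit, by a subject who then attends only the early termination visit. Rash and early symptomatic adverse events are the likeliest examples.

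**How far a mean could move**

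Inputs from the protocol: each subject takes two active doses and one placebo dose. A 12-subject part has at most 24 active and 12 placebo ratings, and a 36-subject Part 1 has at most 72 active ratings. Inputs that are assumed: a mean of 70 among retained ratings and a lost score of 20, so a gap D of 50 points.

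With n ratings due and k lost, the mean of the retained ratings exceeds the mean of all ratings by k × D / n.

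- One active rating lost of 24: the full mean is (23 × 70 + 20)/24 = 67.9, an overstatement of 50/24 = 2.1.
- Two lost of 24: (22 × 70 + 2 × 20)/24 = 65.8, an overstatement of 4.2.
- One active rating lost of 72: 50/72 = 0.7.
- One placebo rating lost of 12: 50/12 = 4.2.
- One active rating lost of 24 with a lost score of 40 (D = 30): (23 × 70 + 40)/24 = 68.75, an overstatement of 1.25.
- No ratings lost, because every stopper attends the Post-Attack visit first: 0.

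**Effect on the active-versus-placebo difference**

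- Loss on active only: the difference moves in favour of active by 2.1 points per rating in a 12-subject part.
- Loss on placebo only: it moves against active by 4.2 points per rating.
- Equal loss per dose, 2 of 24 active and 1 of 12 placebo: both means rise by 4.2 and the difference does not change.

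The sign therefore depends on the proportion lost in each arm and on how low those scores would have been. The documents give neither.

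**The case against.** The strongest reply is that the protocol already asks for the score. Section 11.2.1 covers every clinic visit after a treated attack, the Table 4 footnote covers every later study visit, and 10.3.5 points to Section 11. On that reading this is an inconsistency in drafting rather than a decision to discard data. That stands as a description of the problem. It does not remove it, because the list and the schedule still tell the site otherwise.

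It can also be said that nothing makes the early termination visit replace the Post-Attack visit, that the TSQM is an other secondary endpoint in an exploratory study, and that adverse events, concomitant medications and the diary are still collected at early termination. All of that is correct and limits the weight of the point.

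A reader might infer more than the documents support:

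- **That anyone who stops after a treated attack leaves that dose unscored.** This does not hold for a subject whose Post-Attack visit has taken place.
- **That the worst-tolerated doses drop out and active treatment therefore looks better against placebo.** Subjects may also stop for noncompliance, ineligibility, intercurrent illness or at the sponsor's request. If the drug works, stops after a poor response would fall more often on placebo, which would understate the drug.
- **That two active doses to one placebo dose puts the loss mainly on active.** Bias in a mean depends on the proportion lost, not the count, and equal loss per dose cancels in the difference.

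**Conclusion.** The point holds as an inconsistency with a practical consequence. Two places omit the TSQM at early termination and others call for it. Where a subject stops between dose 1 or 2 and its Post-Attack visit and attends only the early termination visit, a site following the list would lose that dose's score.

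The loss is likely to be informative, but the direction of bias in the active-versus-placebo difference is undetermined. For active versus current therapy, the comparator is rated at Baseline and is not exposed to this loss. If the lost active scores are low, nothing on the other side would offset the inflated active mean.

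The size is unknown. The shifts of about 2 points per lost active rating with 24 ratings, 0.7 with 72, and about 4 per lost placebo rating with 12 all rest on the assumed 50-point gap and on simple means. Section 13.3.5 does not name the model, and no loss rate is given, so zero loss is possible. The correction is worth making because it is cheap and the data cannot be recovered later. It does not bear on the main efficacy or safety conclusions.

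**What to change.** Add the TSQM to the 10.3.5 list and mark it in the Early Termination column of Table 4, to be completed for the latest attack treated with study drug when no TSQM has yet been given for that attack. Worded this way, it works whether or not the early termination visit replaces the Post-Attack visit, and it avoids a second rating of the same dose. Align both places with 11.2.1 and the Table 4 footnote. State in 13.3.5 that these scores are analysed under the treatment given for that attack.

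The cost is one short questionnaire at a visit that already takes place, plus the wording changes. No extra visit or procedure is needed.
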